3.9 Discontinuation of investigational product

Patients may be discontinued from IP in the following situations:

- Patient decision. The patient is at any time free to discontinue treatment, without prejudice to further treatment.
- Adverse event.
- Severe non-compliance with the study protocol.
- Worsened condition.
- Progressive disease.
- Pregnancy.

- Incorrectly enrolled patients.
- The Investigator believes they are no longer deriving clinical benefit (Part B and continued access).

3.9.1 Procedures for discontinuation of a patient from investigational product

At any time, patients are free to discontinue IP or withdraw from the study (ie, IP and assessments – see Section 3.10), without prejudice to further treatment. A patient that decides to discontinue IP will always be asked about the reason(s) and the presence of any AEs. If possible, they will be seen and assessed by an Investigator(s). Adverse events will be followed up (See Section 6); and all study drugs should be returned by the patient.

In Part A and Part B, any patient discontinuing IP should be seen at 30 days (± 7 days) after their last dose for the evaluations outlined in the study plan (see Table 1 and Table 2). After discontinuation of study drug, the Investigator will perform the best possible observation(s), test(s), and evaluation(s), as well as give appropriate medication and all possible measures for the safety of the patient. In addition, they will record on the eCRF the date of discontinuation, the reasons, manifestation, and treatment at the time of discontinuation. If patients discontinue IP, the AstraZeneca monitor or its representative must be informed immediately. The patient should return all IP.

After discontinuation of the study drug in Part A or Part B, all ongoing AEs or SAEs must be followed until resolution unless, in the Investigator's opinion, the condition is unlikely to resolve due to the patient's underlying disease, or the patient is lost to follow-up (see Sections 6.3.1 and 6.3.2). All new AEs and SAEs occurring during the 30 calendar days after the last dose of study drug must be reported (if SAEs, they must be reported to AstraZeneca or its representative within 24 hours as described in Section 6.4) and followed to resolution as above. Patients should attend for a follow-up visit 30 (± 7) days after discontinuing study drug to collect and/or complete adverse event (AE) information and collect IP. Any untoward event occurring subsequent to the 30-day follow-up AE reporting period that the Investigator assesses as possibly related to the study drug should also be reported as an AE.

At the end of Part B, patients may continue to receive IP as continued access and undergo follow up as part of their normal routine clinical care. After discontinuation of the IP in the continued access phase of the study, patients should be followed for 30 days to follow up any existing SAEs and monitor for any new SAEs that may be related to IP.

If a patient is withdrawn from study, see Section 3.10.

3.10 Criteria for withdrawal

3.10.1 Screen failures

Screening failures are patients who do not fulfil the eligibility criteria for the study, and therefore must not be treated. These patients should have the reason for study withdrawal recorded as 'Eligibility Criteria Not Fulfilled' (ie, patient does not meet the required inclusion

criteria or meets exclusion criteria). This reason for study withdrawal is only valid for screen failures.

3.10.2 Withdrawal of the informed consent

Patients are at any time free to withdraw from the study (IP and assessments), without prejudice to further treatment (withdrawal of consent). Patients may withdraw from any aspects of the optional genetics research (see Sections 3.1 and 5.6) at any time, without prejudice to further treatment and independent of any decision concerning participation in other aspects of the main study.

Patients will always be asked about the reasons and the presence of any AEs. If possible, they will be seen and assessed by an Investigator. Adverse events will be followed up (see Section 6.3.2) and diaries and all study drug should be returned by the patient.

If a patient withdraws from participation in the study, then his/her enrolment code cannot be reused.

Patients may be withdrawn from the study for the following reasons:

- Voluntary withdrawal by the patient who is at any time free to discontinue their participation in the study, without prejudice to further treatment.
- Risk to patients as judged by the Investigator and/or AstraZeneca or its representative.
- Severe non-compliance to protocol as judged by the Investigator and/or AstraZeneca or its representative.
- Incorrectly enrolled patients, ie, the patient does not meet the required inclusion/exclusion criteria for the study.
- The patient becomes pregnant.
- Patient is lost to follow-up.

If a patient wishes to withdraw their consent to further participation in the study entirely this should be clearly documented in the patient notes and in the clinical study database.

3.11 Discontinuation of the study

The study may be stopped if, in the judgment of AstraZeneca, study patients are placed at undue risk because of clinically significant findings that:

- meet individual stopping criteria or are otherwise considered significant
- are assessed as causally related to study drug

- are not considered to be consistent with continuation of the study.

Regardless of the reason for termination, all data available for the patient at the time of discontinuation or follow-up must be recorded in the eCRF. All reasons for discontinuation of treatment must be documented.

In terminating the study, the Sponsor will ensure that adequate consideration is given to the protection of the patients' interests.

4. STUDY PLAN AND TIMING OF PROCEDURES

Table 1 Study Plan – Part A

Assessments	Screening	Treatment Period 1					Treatment Period 2				Treatment Period 3				Follow-up ^a			
Visits	1	2	3	4	5	6	7	8	9	10	11	12	13	100				
Day ^b	-28 to -2 days before dosing	-1 ^b	1 ±1	7 ±1	14 ±1	21 ±1	28 ±1	29	35 ±1	42 ±1	49 ±1	50	56 ±1	63 ±1	70 ±1	77 ±1	78	30 (±7) days after last dose
Resident in clinic							<-----> ^c			<-----> ^c					<-----> ^c			
Outpatient visits	X	X	X	X	X	X			X	X			X	X	X			X
Written informed consent	X																	
Demography and baseline characteristics	X																	
Medical/surgical history	X																	
Inclusion/exclusion criteria	X																	
ECOG performance status	X																	
Height and weight	X		X ^d				X ^d				X ^d					X ^d		
Ophthalmologic examination	X																	
Physical examination	X	X					X ^o				X ^o						X	X
Vital signs (BP/pulse) ^e	X						X				X					X		X
Body temperature	X	X	X				X				X					X		X
Resting standard 12-lead ECG ^e	X						X				X					X		X
Echo/MUGA	X																	X
HBV and HCV Serology	X																	
Haematology/coagulation ^f / biochemistry	X	X		X	X	X	X		X	X	X		X	X	X		X	X
Urinalysis ^g	X	X		X	X	X	X		X	X	X		X	X	X		X	X
Serum/urine pregnancy test ^h	X		X				X				X					X		X

Assessments	Screening	Treatment Period 1					Treatment Period 2					Treatment Period 3					Follow-up ^a	
Visits	1	2	3	4	5	6	7	8	9	10	11	12	13	100				
Day ^b	-28 to -2 days before dosing	-1 ^b	1	7 ±1	14 ±1	21 ±1	28 ±1	29	35 ±1	42 ±1	49 ±1	50	56 ±1	63 ±1	70 ±1	77 ±1	78	30 (±7) days after last dose
Resident in clinic						<-----> ^c			<-----> ^c				<-----> ^c					
Outpatient visits	X	X	X	X	X			X	X			X	X	X				X
Pharmacogenetics blood sample ⁱ		X																
AZD9291 administration ^j			X	X	X	X	X	X	X	X	X	X	X	X	X	X		
Rifampicin administration ^k							X	X	X	X								
Diary			P	C	C	C	C		C	C	C		C	C	C	C		
AZD9291 PK blood sampling ^l				X	X	X	X	X	X	X	X	X	X	X	X	X	X	
Rifampicin blood sampling ^m								X	X	X	X							
Blood sample for 4β-hydroxycholesterol			X			X	X				X				X	X		
Prior and concomitant meds	X	X	X	X	X	X	X	X	X	X	X	X	X	X	X	X	X	X
Adverse events ⁿ	X	X	X	X	X	X	X	X	X	X	X	X	X	X	X	X	X	X
AZD9291 dispensed/returned			X				X				X					X		

^a For patients who withdraw from the study prematurely and do not go on to Part B.

^b Day 1 is the day of dosing; Day -1 is the day before dosing. All Day -1 procedures must be performed on Day -1 or pre-dose on Day 1 provided the results are reviewed before dosing. If the patient has been screened within 48 hours of Day 1, safety laboratory tests (haematology, coagulation, biochemistry and urinalysis) do not need to be repeated.

^c Patients will check into the clinic on the morning of Day 28, Day 49 and Day 77 and be prepared to stay overnight for 24 hours serial blood collections and safety assessments.

^d Height to be assessed at Screening only. Weight to be assessed at all timepoints; the same weighing scales should be used at each visit. For height and weight, indoor clothing may be worn but shoes should be removed.

^e Supine BP and pulse will be measured pre-dose, using a semi automatic BP recording device with an appropriate cuff size after the patient has been resting in bed for 10 minutes. For ECG, patients will rest at least 10 minutes before the start of each ECG recording and they must be in the same supine (maximum 30 degrees flexion in the hip and feet not in contact with the footboard) body position at each recording timepoint. On Days 28, 49 and 77, assessments will be performed pre-dose and at 3, 6 and 12 hours post-dose.

- ^f For haematology and clinical chemistry tests, see [Table 4](#). Coagulation (aPTT and INR) will be performed at Screening and if clinically indicated. For patients taking warfarin reference Section [7.7](#).
- ^g Protein, blood and glucose; microscopic analysis is to be performed if required.
- ^h Pre-menopausal women of childbearing potential must have a negative urine or serum pregnancy test within 28 days prior to starting treatment and a confirmatory test before treatment at Visit 1. In the event of suspected pregnancy during the study, the test should be repeated and, if positive, the patient discontinued from study treatment immediately. Pregnancy test will be repeated at the follow-up 30 (± 7) days after last dose of study medication.
- ⁱ Patients will be invited to participate in optional genetic research. The patient must provide separate informed consent. If the patient declines to consent to the optional genetic research, this will not exclude the patient from participating in any other aspect of the study.
- ^j Patients will take AZD9291 80 mg once daily fasted from Day 1 to Day 77. Doses on Day 28, Day 49, and Day 77 will be administered at the clinic by clinic personnel. AZD9291 will be administered fasted from at least 2 hours before dosing to at least 2 hours after dosing. The study treatments should be swallowed whole with approximately 240 mL of water, and not chewed, crushed, dissolved or divided. On Days 28, 49, and 77, water can be allowed as desired except for 1 hour before and after AZD9291 administration. On all other study days there are no water restrictions. The same fasting restrictions apply to self-administered doses.
- ^k Patients will take 600 mg rifampicin once daily from Day 29 to Day 49. In Period 2, doses from Day 29 until Day 48 will be self-administered by the patients. The doses on Day 49 (Period 2 Day 21) will be administered at the clinic by clinic personnel. All rifampicin doses should be taken fasted from at least 2 hours before dosing to at least 2 hours after dosing.
- ^l AZD9291 PK samples will be collected at the times specified in [Table 3](#).
- ^m Rifampicin PK samples will be collected at the times specified in [Table 3](#).
- ⁿ If a patient withdraws for any reason, any ongoing study-related toxicity or SAE at discontinuation must be monitored until resolution. After discontinuation from treatment, patients must be followed up for any new AEs for 30 calendar days after the last dose of study drug. Any existing and any new AEs occurring during the 30-day period must be recorded and followed to resolution if possible.
- ^o Brief physical examination (including general appearance, skin, abdomen, cardiovascular system, and lungs).

AE adverse event; aPTT activated partial thromboplastin time BP blood pressure; C check diary; ECG electrocardiogram; ECOG Eastern Cooperative Oncology Group; HBV Hepatitis B; HCV Hepatitis C virus; INR international normalised ratio; IP investigational product; MUGA multiple gated acquisition scan; P provide diary; PK pharmacokinetics; SAE serious adverse event

Table 2 Study Plan – Part B

Visit Number/Day	Visit 13, Day 77, Part A ^a	Visit 101/Day 84	Visit 102/Day 91	Visit 103/Day 98	Visit 104/Day 105	Subsequent on-treatment visits every 4 weeks ^b Visit 105 onwards Day 1 of next visit period (Equals Day 133 [Week 19] etc)	Follow-up 30 (±7) days after IP permanently discontinued in Part B ^c
Visit window		±3d	±3d	±3d	±3d	±7d	±7d
Physical examination ^d		X	X	X	X	X	X
Vital signs (BP, pulse, temperature, weight) ^e		X	X	X	X	X	X
Haematology/clinical chemistry		X	X	X	X	X	X
Serum/urine pregnancy test ^f	<-----> ^f						X
Resting standard 12-lead ECG ^e						X	X
Echo/MUGA		X				X ^g	X ^g
Adverse events		X	X	X	X	X	X
Concomitant medications		X	X	X	X	X	X
AZD9291 dispensed/returned ^h	X ⁱ				X ^h	X ^h	
Disease status ^j	<-----> ^j						

^a The last visit in Part A (Visit 13, Day 77) will serve as the first visit in Part B.

^b Visit to take place on Day 1 of a 4-week (28-day) visit period. Visits will continue for approximately 12 months from the date the last patient enters Part B. Patients who continue receiving AZD9291 after Part B (continued access) should have their final on-treatment visit within 4 weeks prior to the end of Part B. No further clinical data will be collected in the study database beyond this time (see Section 7.8).

^c Follow-up assessments will only be performed for patients who permanently discontinue AZD9291 treatment during Part B.

^d After baseline, it is not necessary to record any physical examination details on the eCRF; any clinically significant changes should be recorded as AEs.

^e Supine BP and pulse will be measured pre-dose, after the patient has been resting in bed for 10 minutes. For ECG, patients will rest at least 10 minutes before the start of each ECG recording and they must be in the same supine (maximum 30 degrees flexion in the hip and feet not in contact with the footboard) body position at each recording timepoint. For weight assessment, indoor clothing may be worn but shoes must be removed; the same weighing scales should be used at each visit.

^f In the event of suspected pregnancy during Part B of the study, the test should be repeated and, if positive, the patient discontinued from study treatment immediately. Pregnancy test will be repeated at the follow-up 30 (±7) days after last dose of study medication.

^g Echo/MUGA to be performed at least every 12 weeks ± 4 weeks: at Visit 106 and then subsequently every 12 weeks ± 4 weeks. Echo/MUGA at follow-up or final on-treatment visit is not required if patients have had one in the previous 6 weeks, as long as their cardiac function is stable. However, if their cardiac function has been unstable or they have had signs or symptoms suggestive of cardiac instability, patients should have Echo/MUGA performed at their follow-up or final on-treatment visit prior to the end of Part B.

^h Sufficient study treatment should be dispensed for at least each treatment period plus overage; however additional treatment can be dispensed to patients to last longer in accordance with local practice.

ⁱ The return and dispensing of AZD9291 should be on the evening of Visit 13 (Day 77).

^j During Part B no efficacy data will be collected, therefore patients will be monitored as per their normal routine clinical schedule.

Revised Clinical Study Protocol
Drug Substance AZD9291
Study Code D5160C00013
Edition Number 2
Date

Note: Urinalysis will be conducted only if clinically indicated.

AE adverse event; BP blood pressure; ECG electrocardiogram; MUGA multiple gated acquisition scan; SAE serious adverse event.

Table 3 **Timing of PK samples – Part A**

Day	Time (hours)	AZD9291 PK blood	Rifampicin PK blood	4 β -hydroxy-cholesterol
Day 1	Pre-dose			+
Day 7	Pre-dose	+		
Day 14	Pre-dose	+		
Day 21	Pre-dose	+		+
Day 28	Pre-dose, 1, 2, 3, 4, 6, 8, 10 and 12	+		+(pre-dose)
Day 29	24 (pre-dose)	+		
Day 35	Pre-dose	+	+	
Day 42	Pre-dose	+	+	
Day 49	Pre-dose, 1, 2, 3, 4, 6, 8, 10 and 12	+	+	+(pre-dose)
Day 50	24 (pre-dose)	+	+	
Day 56	Pre-dose	+		
Day 63	Pre-dose	+		
Day 70	Pre-dose	+		+
Day 77	Pre-dose, 1, 2, 3, 4, 6, 8, 10 and 12	+		+(pre-dose)
Day 78	24 (pre-dose)	+		

Note: AZD9291 80 mg will be administered once daily on Days 1 to 77
Rifampicin 600 mg will be administered on Days 29 to 49.
See Section 4.2 for a description of the sampling windows around the PK samples.

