1.4 Study design

This is a Phase I, open-label, non-randomised, two-part study in patients with EGFRm+ NSCLC who have progressed on an EGFR TKI. Part A will assess the effect of rifampicin on the PK parameters of AZD9291 and metabolites AZ5104 and AZ7550 following multiple oral dosing of both rifampicin and AZD9291 in a fasted state.

Part B will allow patients further access to AZD9291 after the PK phase (Part A) and will provide for additional safety data collection.

This study will be conducted at approximately 16 sites across Asia, North America and Western Europe with approximately 38 patients enrolled and dosed to achieve at least 30 evaluable patients. Additional patients may be enrolled to ensure the minimum number of evaluable patients. For a patient to be evaluable the patient must have completed the required PK collections for the primary comparison (AZD9291 and rifampicin combined [Period 2] compared to AZD9291 administered alone [Period 1]).

Part A

[figure not shown]
Part A is a non-randomised, open-label, 3-period design. A study flow chart for Part A is presented in [Figure 1](#). Patients will receive AZD9291 80 mg once daily for 77 days (Days 1 to 77). Patients will also receive oral daily doses of rifampicin for 21 days (Days 29 to 49) concurrently with AZD9291.

Part B

On completion of Part A, patients may continue to take AZD9291 tablets (80 mg once daily) in Part B if they and the Investigator agree that this is appropriate. Patients should start Part B immediately (ie, 24 hours) after the last dose received in Part A (Day 78 after the 24-hour sample collection). Patients will have weekly clinic visits for the first 4 weeks; thereafter visits will be every 4 weeks. Safety assessments will be collected and there will be no formal evaluation of efficacy. Patients' medical/oncological care will be according to local clinical practice. Part B will be of approximately 12 months' duration from the date the last patient enters this part of the study (allowing for any scheduled Part B follow-up assessments).

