During and after Part B, patients may continue to take AZD9291, if they and the Investigator deem it appropriate, until such time as the Investigator believes they are no longer deriving clinical benefit or they stop taking AZD9291 for any other reason. After the end of Part B (approximately 12 months after the last patient entered Part B), patients will be seen as per their normal routine clinical schedule. No clinical data will be collected for those patients who continue to receive AZD9291 as part of continued access, other than the data specified in [Section 7.8](#).

Figure 1 Study flow chart – Part A

^a For patients who withdraw from the study prematurely and who do not participate in Part B

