4.3 Follow-up period

Patients will return to the clinic for follow-up assessments 30 days (± 7 days) after their last dose, regardless of whether the last dose was in Part A or Part B. Follow-up assessments for Part A are detailed in Table 1; follow-up assessments for Part B are detailed in Table 2.

If the patient's last dose of AZD9291 is in the continued access phase (after Part B), the patient should be contacted 30 days after their last dose of AZD9291 to follow up any existing SAEs and monitor for new SAEs that may be related to IP.

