5.2.5 Echocardiogram/MUGA scan

An echocardiogram or MUGA scan to assess left ventricular ejection fraction (LVEF [%]) will be performed at screening and at the visits indicated in [Table 1](#) and [Table 2](#). The modality of the cardiac function assessments must be consistent within a patient, ie, if an echocardiogram is used for the screening assessment then an echocardiogram should also be used for subsequent scans. The patients should also be examined using the same machine and operator whenever possible. The LVEF value (%) should be recorded on the eCRF.

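### Two footnotes limit the Part A follow-up visit to premature withdrawals, against Section 4.3, so patients who complete Part A and decline Part B could have no LVEF value after screening

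*Protocol*

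**What the plan says.** The protocol gives two different rules for who attends the 30-day follow-up visit after Part A.

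The body text is broad. Section 4.3 has patients return 30 (±7) days after their last dose "regardless of whether the last dose was in Part A or Part B" and refers to Table 1 for the Part A assessments. Section 3.9.1 points the same way: "In Part A and Part B, any patient discontinuing IP should be seen at 30 days".

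The schedule is narrow. The follow-up column of Table 1 (Visit 100) carries footnote a: "For patients who withdraw from the study prematurely and do not go on to Part B". The footnote under Figure 1 in Section 1.4 repeats the limit: "For patients who withdraw from the study prematurely and who do not participate in Part B".

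Three other provisions matter:

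- **Part B is optional.** Section 1.4 says that, once Part A is complete, "patients may continue to take AZD9291 tablets (80 mg once daily) in Part B if they and the Investigator agree that this is appropriate".
- **Table 2 has its own follow-up rule.** Its footnote c reads: "Follow-up assessments will only be performed for patients who permanently discontinue AZD9291 treatment during Part B".
- **Section 5.2.5 sets no separate timing for Echo/MUGA.** The scan "will be performed at screening and at the visits indicated in" Tables 1 and 2.

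**The concern.** The footnotes join two conditions: leaving the study early and not entering Part B. A patient who takes the full 77-day course and then declines Part B meets only the second. Section 4.3 gives that patient the visit and the footnotes take it away. Section 4.3 itself sends sites to Table 1, and a site scheduling visits will probably work from that table.

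The main thing at stake is cardiac safety data. Echo/MUGA is a listed safety outcome for Part A, and Visit 100 is the only Part A time point for it after screening. The patient would also lose the off-treatment ECG, vital signs, physical examination and laboratory tests. As a result, someone who completed all of Part A would be followed less closely than someone who left early.

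**Working it through.** No sample size, power or alpha figure is involved. The check is a comparison of the rules and a count of the schedule entries.

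**Step 1: routes out of Part A, and the next scheduled Echo/MUGA if the footnotes are followed**

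| Route | Next Echo/MUGA | Source |
|---|---|---|
| Leaves early, does not enter Part B | Visit 100 | Table 1, footnote a |
| Enters Part B | Visit 101 (Day 84) | Table 2 |
| Completes Day 77/78, declines Part B | None | Outside Table 1 footnote a and Table 2 footnote c |

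Under Section 4.3 the third route also leads to Visit 100. With a last dose on Day 77 the window is 77 + 30 ± 7, that is Day 100 to Day 114.

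**Step 2: the Echo/MUGA row of Table 1**

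Of the 18 day columns, two are marked: screening and follow-up. Nothing is marked from Day -1 to Day 78. For a completer who declines Part B, the number of post-screening scans is 1 under Section 4.3 and 0 under footnote a. One of the two Part A LVEF assessments is lost, and it is the only one after dosing starts.

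**Step 3: what else Visit 100 carries**

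Table 1 marks ten assessments there. For each, the last on-treatment entry is:

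- Day 77: vital signs, temperature, ECG, pregnancy test (4)
- Day 78: physical examination, haematology/biochemistry, urinalysis (3)
- Days 77 and 78: concomitant medications, adverse events (2)
- None after screening: Echo/MUGA (1)

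So 4 + 3 + 2 = 9 of the ten have an end-of-treatment value, and 10 − 9 = 1 does not. Two of the nine are also called for after the last dose by other footnotes. Footnote n covers adverse events ("After discontinuation from treatment, patients must be followed up for any new AEs for 30 calendar days after the last dose of study drug"), and footnote h asks for the pregnancy test at follow-up.

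**Step 4: the protocol's own standard in Part B**

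Table 2 footnote g waives the follow-up or final on-treatment scan only if one was done in the previous 6 weeks and cardiac function is stable. Screening runs from 28 to 2 days before Day 1, and Day 77 is 76 days after Day 1. At Day 77 the screening scan is therefore between 2 + 76 = 78 days (78/7 = 11.1 weeks) and 28 + 76 = 104 days (104/7 = 14.9 weeks) old, and it predates all treatment. It would not meet the 6-week condition.

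**The case against.** The strongest reply is that Section 4.3 is the section written to govern follow-up and its rule is clear, so the visit is missed only if a site lets a footnote override it. Other text agrees with Section 4.3. Section 5.2.1 places the pregnancy test at follow-up in either part, and Section 5.2.3 lists a physical examination at follow-up without restriction. This limits the consequence but leaves the contradiction, because Section 4.3 relies on the table whose footnote narrows the visit.

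A second reply is that the study spans Part A, Part B and continued access, so a patient who stops at Day 78 might be said to have left it prematurely. That reading is possible but strained. Part B is optional, Section 3.10.2 uses withdrawal from the study to mean stopping both treatment and assessments, and Section 3.3 separates leaving Part A from leaving the study. Someone who has completed everything Part A asks has not withdrawn early in that sense.

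A third reply concerns Section 3.9.1, and it has force. If finishing the planned 77 days does not count as discontinuing the product, Section 3.9.1 does not contradict the footnotes. By the same reading, neither it nor footnote n would secure 30-day adverse event follow-up for this patient. If finishing does count, Section 3.9.1 requires the full visit. It is best treated as supporting evidence. The firm contradiction is with Section 4.3.

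It is also fair to say that the practical loss comes down mainly to one LVEF reading in an unknown, possibly small, number of patients.

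**Conclusion.** The concern holds, as a minor error in the document as written. Table 1 footnote a and the Figure 1 footnote contradict Section 4.3 on whether a patient who completes Part A and declines Part B attends Visit 100, and no other provision of the schedule fills the gap. If the footnotes are followed, such a patient has no LVEF value after screening, and Echo/MUGA is the only one of the ten Visit 100 assessments left without an end-of-treatment value.

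The size rests on two things that the protocol does not settle: how many patients complete Day 77/78 and decline Part B, and how many sites would follow the footnote over Section 4.3. The Day 77/78 safety data and the primary Period 2 versus Period 1 PK comparison are not touched.

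**What to change.** Reword footnote a of Table 1 and the footnote under Figure 1 to: *For all patients whose last dose of AZD9291 is in Part A (completed or discontinued prematurely) and who do not enter Part B.* This brings both into line with Section 4.3, and with Section 3.9.1 on its broader reading.

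The cost is the wording of two footnotes. No visit, procedure or patient is added beyond what Section 4.3 already requires, and no analysis changes.
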